5.9.2 Plasma PK Parameters

PK parameters will not be estimated for this study as no participants from Part A agreed to participate in the optional overnight PK sampling.

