^c Including CBC, clinical chemistry, coagulation factors, viral serology screen, exploratory urine biomarkers, urinalysis and urine albumin. Coagulation factors and viral serology screen collected at Screening only.

^d Triplicate measurement will be taken at Screening only; for all other timepoints, single measurement is acceptable.

^e Screening, Day 0 and Day 21: completed anytime; Day 1, pre-dose (if not done on Day 0) and 6 (±2) hours post-dose; Day 7 and Day 14, 6 (±2) hours post-dose.

Visit Days	Day -28 to Day -1 (Screening)	Day 0* (Baseline)	Day 1	Day 7 (±1)	Day 14 (±1)	Day 21 (±1) End of Clinical Trial or Early Termination
------------	-------------------------------	-------------------	-------	------------	-------------	--

^fThe TETRAS Performance assessment will be captured on video for central reading. The local rater will rate the same TETRAS Performance assessment that is captured on video. The Screening video will be independently assessed for eligibility.

^gTo be performed 2 consecutive times separated by at least 30 minutes, the first of the two accelerometer assessments should be completed immediately after the TETRAS Performance assessment. All 3 maneuvers in the upper limb item (sub-items 4a, 4b, and 4c) will be completed for both arms, first for the RIGHT arm and then for the LEFT.

^hDay 1: 0 (pre-dose); Day 1, 7 and 14; post-dose immediately after completion of the 2nd accelerometer-based upper limb assessment; When PK sampling timepoints coincide with the TETRAS Performance timepoints or accelerometer-based assessment timepoints the PK sample is to be obtained last.

ⁱOptional samples collected at sites that have capabilities to perform serial sample collection: Day 1, 7 and 14: 0 (pre-dose), 0.5, 1, 2, 3, 4, 6, 8, 10, 12, 24 hours post-dose. All collection times up to 4 hours post-dose have a ±15 min window and a ±30 min window thereafter. 24-hour timepoint samples are to be taken prior to the AM dose. When PK sampling timepoints coincide with the TETRAS Performance timepoints or accelerometer-based assessment timepoints the PK sample is to be obtained last.

^jAdministered in clinic on Day 1. All other days it should be taken in the morning, within 30 minutes after breakfast. On Day 1 participant should be observed in clinic for approximately 6 hours before discharge. Study drug is dispensed (20 mg QAM for Day 1 to Day 7; 40 mg QAM for Day 8 to Day 14).

Table 3: Schedule of Activities (SoA) – Part B

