^b Vital signs include pulse rate, respiratory rate, temperature, and blood pressure. Blood pressure must be measured once after the participant has been supine for at least 5 minutes and once after the participant has been standing for at least 2 minutes. On Day 1, vital signs should be measured pre-dose, 2 hours post-dose (±30 min), and 6 hours post-dose (±30 min).

^c Including CBC, clinical chemistry, coagulation factors, viral serology screen, urinalysis, and urine albumin. Coagulation factors and viral serology screen collected at Screening only.

^d A triplicate measurement must be taken at Screening only; for all other timepoints, a single measurement is acceptable.

^e TETRAS can be completed anytime at Screening and Day 70. On other days, the following timing should be followed:

Day 1: pre-dose and 6 (±2) hours after a 20 mg QAM dose

Day 7: 6 (±2) hours after a 40 mg QAM dose

Day 21: 6 (±2) hours after an 80 mg (or highest tolerated dose) QAM dose

Day 42: pre-dose and 6 (±2) hours after a 120 mg (or highest tolerated dose) QAM dose

Day 56: 6 (±2) hours post-dose

^f The TETRAS Performance assessment will be captured on video for central reading. The local rater must rate the same TETRAS Performance assessment as that which is captured on video for central reading. The Screening video will also be independently assessed for eligibility.

^g Kinesia ONE assessments must be completed immediately after the TETRAS Performance assessments (including both pre-dose and post-dose assessments on Day 1 and Day 42). After each TETRAS Performance assessment, Kinesia ONE assessments should be completed twice separated by at least 30 minutes. All 3 maneuvers in the upper limb item (sub-items 4a, 4b, and 4c) will be completed for both arms, first for the RIGHT arm and then for the LEFT.

^h For visits with multiple TETRAS assessments, the TETRAS ADL subscale should only be assessed once. On Day 1, the ADL subscale should be completed pre-dose. On day 42, the ADL subscale should be completed 6 (±2) hours after the QAM dose.

ⁱ On Day 1 and Day 42 blood samples should be collected at the following timepoints: pre-dose and 0.5, 1, 2, 4, and 6 hours post-dose. The 6-hour post-dose sample will be collected immediately after completion of the second Kinesia ONE assessment. When PK sampling timepoints coincide with the TETRAS

Study Phase	Screening		Open-label Titration								Double-Blind Randomized Withdrawal	Safety Follow-up	

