Visit Days (Visit Window)	Day -28 to Day -1		Day 1 (Baseline)	Day 3	Day 7	Day 14	Day 21	Day 28	Day 35	Day 41	Day 42	Day 56	Day 70/ET (End of Clinical Trial)
		Day -2 (-2)											

Performance timepoints or accelerometer-based assessment timepoints, the PK sample is to be obtained last. On Days 7, 21, and 56; samples should be collected 2 hours post-dose. Blood collection can be completed anytime on Day 70.

^j Participants will be randomized (1:1) to receive either placebo or PRAX-944 from Day 43 to Day 56. Randomization can occur on Day 37 through Day 42.

^k On Day 1 and 42, study drug must be administered in the clinic on an empty stomach (at least 1 hour before breakfast, which will be provided at the site) and the participant should be observed in the clinic for approximately 6 hours before discharge. On all other days, participants should be instructed to take study drug at least 1 hour before breakfast in the morning at home. The escalation schedule is as follows: 20 mg, Day 1 through Day 3; 40 mg, Day 4 through Day 7; 60 mg, Day 8 through Day 14; 80 mg, Day 15 through Day 21; 100 mg, Day 22 through Day 28; and 120 mg, Day 29 through Day 42. Participants will receive blinded study drug on Days 43 to 56. During blinded treatment period, participants should take the same number of tablets per day as taken during Days 36 to 42.

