3. OBJECTIVES AND ENDPOINTS

To evaluate the efficacy, safety, tolerability, and pharmacokinetics (PK) of PRAX-944 in adults with ET.

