5.9 Pharmacokinetic Analyses

5.9.1 Plasma Concentrations

For each study part, plasma concentrations will be summarized by visit and nominal sampling time using descriptive statistics. For concentration summaries, plasma concentrations below the level of quantification (BLQ) will be set to zero. Descriptive statistics for plasma concentrations will include n, number of participants with concentrations below the level of quantification (BLQ), mean, SD, coefficient of variation (CV%), geometric CV%, geometric mean, median, minimum, and maximum. All plasma concentration data will be listed by study part, participant, and visit.

Plasma concentrations will also be presented graphically.

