7 CHANGES TO PLANNED ANALYSES

7.1 Changes to Analysis as Described in Protocol

The protocol specifies an exploratory objective “to characterize the pharmacokinetic (PK) profile of PRAX-944 following multiple dose administration” for Part A. This objective will not be assessed as no participants from Part A agreed to participate in the optional overnight PK sampling.

The order of the endpoints supporting the objective “to evaluate the duration of PRAX-944 effect on upper limb tremor, other measures of tremor severity, measures of disease impact, mood, and global measures of disease state in participants with ET” as specified in the protocol has been updated to reflect the importance of direct measures of movement (ie, accelerometry) and activities of daily living.

The protocol includes a Day 0 (Baseline) visit in the SoA for Part A. However, for simplicity and consistency across both parts of the study, the derived study day variable as defined in [Section 4](#) will not include a study day 0.

The TETRAS combined upper limb score (derived as the sum of the 6 TETRAS upper limb sub-items, the handwriting item, and the spirals item scores) has been included as another TETRAS based measure of upper limb tremor.

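### SAP 5.9.2 drops PK parameters study-wide for a reason that applies only to Part A, and the Part B concentrations that remain are pooled across doses and, on Day 56, across placebo and active

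*SAP*

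**What the plan says.** **Aim.** Protocol section 3 gives the overall aim as "To evaluate the efficacy, safety, tolerability, and pharmacokinetics (PK) of PRAX-944 in adults with ET". The visible primary and secondary endpoints of both parts contain no PK endpoint.

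**Parameters.** Protocol 9.3.3 plans noncompartmental parameters for Part A, allows others to be added, and leaves the final list to the SAP or a separate PK analysis plan. For Part B, the synopsis (Statistical Methods) plans a summary of concentration-time data only. SAP 5.9.2 then says "PK parameters will not be estimated for this study as no participants from Part A agreed to participate in the optional overnight PK sampling". SAP 7.1 drops the Part A exploratory PK objective on the same ground: "This objective will not be assessed as no participants from Part A agreed to participate in the optional overnight PK sampling". SAP 4.11 still says that Part A parameters for parent drug and three metabolites will be estimated.

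**Sampling.** The Part A serial schedule was optional and ran over 24 hours: "Day 1, 7 and 14: 0 (pre-dose), 0.5, 1, 2, 3, 4, 6, 8, 10, 12, 24 hours post-dose". In Part B, Protocol Table 3 footnote i says "On Day 1 and Day 42 blood samples should be collected at the following timepoints: pre-dose and 0.5, 1, 2, 4, and 6 hours" post-dose, and the SAP's Appendix 1 repeats it. The same footnote adds "On Days 7, 21, and 56; samples should be collected 2 hours post-dose".

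**What is reported.** SAP 5.9.1: for each study part, "plasma concentrations will be summarized by visit and nominal sampling time using descriptive statistics", with values below quantification set to zero. SAP section 5 presents PK for Part B as a whole, not by phase, in one PRAX-944 column.

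**The concern.** Two things look wrong.

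First, the reason and its scope do not match. Refusal of overnight sampling in Part A says nothing about Part B, which has its own scheduled sampling, a higher dose range (up to 120 mg against 40 mg) and different dosing conditions (before breakfast against after it). The SAP does not say why Part B yields no parameters.

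Second, the summary that remains cannot be tied to a dose at the later visits. Protocol 4.1.2.2.1 and 6.6 allow one return to a lower dose, so participants at the same visit can be on different doses. On Day 56 the single column also takes in those randomised to placebo, whereas Protocol 9.3 asks for the randomised portion to be summarised by randomised treatment. SAP 7.1 does not list this as a departure.

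At stake is whether the report of the first trial of this drug in essential tremor can state exposure at a given dose.

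**Working it through.** No figure in the plan needs reproducing. The check compares what the samples can support with what is reported, then sizes the pooling.

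**Samples per participant**
- Part A without the optional profile: 2 (Day 1) + 1 (Day 7) + 1 (Day 14) = 4. This is too few for noncompartmental parameters, so 5.9.2 is right for Part A.
- Part B completer: 6 (Day 1) + 1 (Day 7) + 1 (Day 21) + 6 (Day 42) + 1 (Day 56) + 1 (Day 70) = 16.
- With 12 to 24 participants and two profiles each, 24 to 48 profiles are scheduled. This is a ceiling: anyone stopping before Day 42 has no second profile.

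**Steady state on Day 42**
- Protocol 5.4.3 equates 5 half-lives with 3 days: 72 h / 5 = 14.4 h.
- No dose change is allowed after Day 36, so at least 6 days at constant dose precede the Day 42 pre-dose sample: 6 × 24 / 14.4 = 10 half-lives. Steady state is plausible.

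**What a 0 to 6 h window supports**
- It covers 6/24 = 25% of the dosing interval and 6/14.4 = 0.42 of a half-life, so t1/2 and Vd/F are not estimable.
- The synopsis says the tablet releases 80% within 7 h, so a peak after 6 h is possible.
- Illustrative one-compartment steady-state model (assumed half-life 5, 10 or 14.4 h; assumed absorption rate 0.15, 0.23, 0.4 or 0.8 per h; 12 scenarios): Tmax 2.6 to 7.7 h, beyond 6 h in 5 of 12. The first 6 h hold 25% to 50% of AUC0-tau.
- Using the Day 42 pre-dose value as the 24 h value, estimated AUC0-tau is 0.90 to 0.99 of the true value with the linear-log rule, and 0.95 to 1.22 with the linear rule.

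**Dose mixing on Day 42** (assumed: linear PK, 30% CV within each dose, concentrations in dose units)
- *4 of 12 at 60 mg, 8 at 120 mg.* Mean = (8×120 + 4×60)/12 = 100, and 100/120 = 0.833, so 17% low. Within-dose variance = (8×36² + 4×18²)/12 = 972. Between-dose variance = (8×20² + 4×40²)/12 = 800. CV = √1772/100 = 42%.
- *1 of 12 at 100 mg, 11 at 120 mg.* Mean = (11×120 + 100)/12 = 118.3, 1.4% low. Variance = 1263 + 30.6 = 1293.6. CV = 36.0/118.3 = 30.4%.

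**Arm mixing on Day 56** (assumed: equal arms, placebo values below quantification)
- The last active dose in the placebo arm is on Day 42: 14 × 24 / 14.4 = 23 half-lives earlier.
- With active mean m and CV 30%, the pooled mean is 0.5m.
- Variance = 0.5 × 1.09m² − 0.25m² = 0.295m². CV = 0.543/0.5 = 109%.
- The geometric mean that SAP 5.9.1 asks for is zero or undefined once zeros enter.

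**Nominal time.** The 6 h sample is taken after the second Kinesia test, at least 30 minutes after the first, which itself follows a TETRAS assessment allowed at 4 to 8 h. Real times can therefore spread over 4 hours or more under one label.

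**The case against.** A reader might infer that the SAP cancels planned Part B parameters, or that the trial's PK aim goes unanswered. The documents support neither. The protocol planned parameters for Part A only and concentration summaries for Part B, and SAP 5.9.1 keeps those for both parts with means, spread, plots and listings. Day 1 of Part B is at 20 mg for everyone, so the early profile is not mixed. Part A allows no dose modification. Protocol 9.3.3 and 9.3.4 leave room for PK-efficacy and population PK analyses, the latter outside the main report. The Part B exploratory objectives are redacted, and a separate PK analysis plan may exist.

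It is also fair to say that Part B parameters would be limited: a window of 6 h in 24 h cannot replace the Part A profile, and reporting concentrations by time is a defensible choice. The 17% and 42% figures are one assumed scenario, and the milder one is negligible. If placebo samples on Day 56 are not assayed, or are left out of the column, the arm mixing disappears.

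All of this stands and makes the point minor. It does not remove the mismatch between reason and scope in 5.9.2, nor the pooling as written. The PK analysis set in SAP 3.6 includes every dosed participant with sufficient data, so those switched to placebo are in it, and nothing in the SAP excludes their Day 56 samples.

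**Conclusion.** The point holds as a minor one. SAP 5.9.2 is sound for Part A and gives no reason for Part B. The PK aim is answered, but at the later Part B visits only by means not tied to a dose. Under linear PK and 30% CV the Day 42 mean is between about 1% and 17% low in the two step-down patterns shown. The true rate is unknown and the documents give none. On Day 56 the pooled mean is about half the active mean, if placebo values are below quantification and set to zero. The 14.4 h half-life is inferred from the contraception text, and the AUC accuracy rests on an assumed model.

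**What to change.** 1. Present Part B Day 21 and Day 42 concentrations by actual dose, or dose-normalised with linearity stated as an assumption, and Day 56 by randomised treatment. SAP 4.8 records dose, and SAP 4.10.1 already assigns adverse events to actual dose level.
2. Limit the reason in 5.9.2 to Part A, and reconcile it with SAP 4.11.
3. From the actual sample times recorded under SAP 4.11, derive for Part B what the window supports: Day 42 trough, AUC0-6, and observed Cmax and Tmax within 6 h. Add an approximate Day 42 AUC0-tau with its steady-state assumption and integration rule stated. Say that t1/2 and Vd/F are not estimable and that a peak after 6 h is truncated. If the sponsor prefers to derive none of these, the SAP should give a reason specific to Part B and say whether population PK will be done.

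Cost: a little extra analysis and a short SAP edit. No new samples or visits are needed.

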6 INTERIM ANALYSES

No formal interim analysis is planned for this clinical trial.

7 CHANGES TO PLANNED ANALYSES

7.1 Changes to Analysis as Described in Protocol

The protocol specifies an exploratory objective “to characterize the pharmacokinetic (PK) profile of PRAX-944 following multiple dose administration” for Part A. This objective will not be assessed as no participants from Part A agreed to participate in the optional overnight PK sampling.

The order of the endpoints supporting the objective “to evaluate the duration of PRAX-944 effect on upper limb tremor, other measures of tremor severity, measures of disease impact, mood, and global measures of disease state in participants with ET” as specified in the protocol has been updated to reflect the importance of direct measures of movement (ie, accelerometry) and activities of daily living.

The protocol includes a Day 0 (Baseline) visit in the SoA for Part A. However, for simplicity and consistency across both parts of the study, the derived study day variable as defined in [Section 4](#) will not include a study day 0.

The TETRAS combined upper limb score (derived as the sum of the 6 TETRAS upper limb sub-items, the handwriting item, and the spirals item scores) has been included as another TETRAS based measure of upper limb tremor.

7.2 Changes to Approved Version of the SAP

Not applicable.

APPENDIX 1 SCHEDULE OF ACTIVITIES**Schedule of Activities for Part A**

Visit Days	Day -28 to Day -1 (Screening)	Day 0* (Baseline)	Day 1	Day 7 (±1)	Day 14 (±1)	Day 21 (±1) End of Clinical Trial or Early Termination
CLINICAL TRIAL ENTRY AND GENERAL ASSESSMENTS						
Informed Consent	X					
Inclusion/ Exclusion	X	X				
Demographic Data	X					
Medical History	X					
Body Weight/ Height	X					
Drug/ Alcohol Screen ^a	X	X				
Pregnancy test	X (serum)	X (urine)				X (urine)
SAFETY ASSESSMENTS						
Vital Signs ^b	X	X	X	X	X	X
Physical Examination	X	X				X
Clinical Laboratory Tests ^c	X	X		X	X	X

12-lead ECG ^d	X	X		X	X	
C-SSRS (Baseline/Screening)	X					
C-SSRS (Since Last Visit)		X		X	X	X
AE Monitoring	X					
Concomitant Meds/ Procedures	X					
EFFICACY ASSESSMENTS						
TETRAS Performance ^e	X	X	X	X	X	X
PHARMACOKINETICS						
Blood Collection for Study Drug Concentration (sparse sampling) ^h			X	X	X	
Blood Collection for Study Drug Concentration (serial sampling) ⁱ			O	O	O	
STUDY DRUG						
Study Drug Administration ^j			X			

AE=adverse event; ██████████ TETRAS=The Essential Tremor Rating Assessment Scale. C-SSRS=Columbia-Suicide Severity Rating Scale; ECG=electrocardiogram; O=optional; ██████████

D

* Day 0 (Baseline) activities may be combined with Day 1 activities, provided that Baseline activities are completed before dosing in the morning.

^a Urine sample for assessment of selected drugs and a breath sample for alcohol screen.

^b Vital signs (pulse rate, respiratory rate, temperature, and blood pressure [after the participant has been supine for at least 5 minutes and standing for at least 2 minutes]). On Day 1, should be performed 2 and 6 hours after dosing (± 30 min).

^c Including CBC, clinical chemistry, coagulation factors, viral serology screen, exploratory urine biomarkers, urinalysis and urine albumin. Coagulation factors and viral serology screen collected at Screening only.

^d Triplicate measurement will be taken at Screening only; for all other timepoints, single measurement is acceptable.

^e Screening, Day 0 and Day 21: completed anytime; Day 1, pre-dose and 6 (± 2) hours post-dose; Day 7 and Day 14 6 (± 2) hours post-dose.

^f The TETRAS Performance assessment will be captured on video for central reading. The local rater will rate the same TETRAS Performance assessment that is captured on video. The Screening video will be independently assessed for eligibility.

^g To be performed 2 consecutive times separated by at least 30 minutes, the first time immediately after the post-dose TETRAS Performance assessment. All 3 maneuvers in the upper limb item (sub- items 4a, 4b, and 4c) will be completed for both arms, first for the RIGHT arm and then for the LEFT.

[figure not shown]
^h Day 1: 0 (pre-dose); post-dose immediately after completion of the 2nd accelerometer-based upper limb assessment; When PK sampling timepoints coincide with the TETRAS Performance timepoints or accelerometer-based assessment timepoints the PK sample is to be obtained last.

ⁱ Optional samples collected at sites that have capabilities to perform serial sample collection: Day 1, 7 and 14: 0 (pre-dose), 0.5, 1, 2, 3, 4, 6, 8, 10, 12, 24 hours post-dose. All collection times up to 4 hours post-dose have a ± 15 min window and a ± 30 min window thereafter. 24-hour timepoint samples are to be taken prior to the AM dose. When PK sampling timepoints coincide with the TETRAS Performance timepoints or accelerometer-based assessment timepoints the PK sample is to be obtained last.

[figure not shown]
^j Administered in clinic on Day 1. All other days it should be taken in the morning, within 30 minutes after breakfast. On Day 1 participant should be observed in clinic for approximately 6 hours before discharge. Study drug is dispensed (20 mg QAM for Day 1 to Day 7; 40 mg QAM for Day 8 to Day 14).

Schedule of Activities for Part B

Study Phase	Screening		Open-label Titration								
	Day -28 to Day -1		Day 1 (Baseline)	Day 3	Day 7	Day 14	Day 21	Day 28	Day 35	Day 41	Day 42
Visit Days (Visit Window)		Day -2 (-2)									
CLINICAL TRIAL ENTRY AND GENERAL ASSESSMENTS											
Informed Consent	X										
Inclusion/Exclusion	X		X*								
Demographic Data	X										
Medical History	X										
Body Weight/Height	X										
Drug/Alcohol Screen ^a	X		X*								
Pregnancy test	X (serum)		X (urine)*								
SAFETY ASSESSMENTS											
Vital Signs ^b	X		X		X		X				X

Study Phase	Screening		Open-label Titration								
	Day -28 to Day -1		Day 1 (Baseline)	Day 3	Day 7	Day 14	Day 21	Day 28	Day 35	Day 41	Day 42
Visit Days (Visit Window)		Day -2 (-2)									
Physical Examination	X		X*								
Clinical Laboratory Tests ^c	X		X*		X		X				X
12-lead ECG ^d	X		X*		X		X				X
C-SSRS (Baseline/Screening)	X										
C-SSRS (Since Last Visit)			X*		X		X				X

Study Phase	Screening		Open-label Titration									[REDACTED]		
Visit Days (Visit Window)	Day -28 to Day -1		Day 1 (Baseline)	Day 3	Day 7	Day 14	Day 21	Day 28	Day 35	Day 41	Day 42			
		Day -2 (-2)												
SAFETY ASSESSMENTS													[REDACTED]	
Phone Call Check-in				X		X		X	X					
AE Monitoring	X													
Concomitant Meds/ Procedures	X													
EFFICACY ASSESMENTS													[REDACTED]	
TETRAS Performance ^c	X		X		X		X				X			
[REDACTED]														

Study Phase	Screening		Open-label Titration									
	Day -28 to Day -1	Day -2 (-2)	Day 1 (Baseline)	Day 3	Day 7	Day 14	Day 21	Day 28	Day 35	Day 41		Day 42
Visit Days (Visit Window)												
QUEST			X		X		X				X	

Study Phase	Screening		Open-label Titration									
	Day -28 to Day -1	Day -2 (-2)	Day 1 (Baseline)	Day 3	Day 7	Day 14	Day 21	Day 28	Day 35	Day 41		Day 42
Visit Days (Visit Window)												
EFFICACY ASSESMENTS												
PHARMACOKINETICS												
Blood Collection for Study Drug Concentration ¹			X		X		X				X	

Study Phase	Screening		Open-label Titration								
Visit Days (Visit Window)	Day -28 to Day -1		Day 1 (Baseline)	Day 3	Day 7	Day 14	Day 21	Day 28	Day 35	Day 41	Day 42
		Day -2 (-2)									
STUDY DRUG											
Randomization ^j											X
Study Drug Dispensing			X		X		X				X
Study Drug Administration ^k				X (open label)							

ADL=Activities of Daily Living; AE=adverse event; ██████████ CBC=complete blood count; ██████████
 ██████████ C-SSRS=Columbia-Suicide Severity Rating Scale; ECG=electrocardiogram; Meds=Medications; ██████████; PK=pharmacokinetics;
 QAM=every morning; QUEST=Quality of Life in Essential Tremor Questionnaire; TETRAS=The Essential Tremor Rating Assessment Scale.

* May be performed on Day -1.

a Urine sample for assessment of selected drugs and a breath sample for alcohol screen.

b Vital signs include pulse rate, respiratory rate, temperature, and blood pressure. Blood pressure must be measured once after the participant has been supine for at least 5 minutes and once after the participant has been standing for at least 2 minutes. On Day 1, vital signs should be measured pre-dose, 2 hours post-dose (±30 min), and 6 hours post-dose (±30 min).

c Including CBC, clinical chemistry, coagulation factors, viral serology screen, urinalysis, and urine albumin. Coagulation factors and viral serology screen collected at Screening only.

d A triplicate measurement must be taken at Screening only; for all other timepoints, a single measurement is acceptable.

e TETRAS can be completed anytime at Screening and Day 70. On other days, the following timing should be followed: Day 1: pre-dose and 6 (±2) hours after a 20 mg QAM dose Day 7: 6 (±2) hours after a 40 mg QAM dose Day 21: 6 (±2) hours after an 80 mg (or highest tolerated dose) QAM dose Day 42: pre-dose and 6 (±2) hours after a 120 mg (or highest tolerated dose) QAM dose Day 56: 6 (±2) hours post-dose

f The TETRAS Performance assessment will be captured on video for central reading. The local rater must rate the same TETRAS Performance assessment as that which is captured on video for central reading. The Screening video will also be independently assessed for eligibility.

Study Phase	Screening		Open-label Titration									
Visit Days (Visit Window)	Day -28 to Day -1		Day 1 (Baseline)	Day 3	Day 7	Day 14	Day 21	Day 28	Day 35	Day 41		Day 42
		Day -2 (-2)										

g Kinesia ONE assessments must be completed immediately after the TETRAS Performance assessments (including both pre-dose and post-dose assessments on Day 1 and Day 42). After each TETRAS Performance assessment, Kinesia ONE assessments should be completed twice separated by at least 30 minutes. All 3 maneuvers in the upper limb item (sub-items 4a, 4b, and 4c) will be completed for both arms, first for the RIGHT arm and then for the LEFT.

h For visits with multiple TETRAS assessments, the TETRAS ADL subscale should only be assessed once. On Day 1, the ADL subscale should be completed pre-dose. On day 42, the ADL subscale should be completed 6 (±2) hours after the QAM dose.

i On Day 1 and Day 42 blood samples should be collected at the following timepoints: pre-dose and 0.5, 1, 2, 4, and 6 hours post-dose. The 6-hour post-dose sample will be collected immediately after completion of the second Kinesia ONE assessment. When PK sampling timepoints coincide with the TETRAS Performance timepoints or accelerometer-based assessment timepoints, the PK sample is to be obtained last. On Days 7, 21, and 56; samples should be collected 2 hours post-dose. Blood collection can be completed anytime on Day 70.

j Participants will be randomized (1:1) to receive either placebo or PRAX-944 from Day 43 to Day 56. Randomization can occur on Day 37 through Day 42.

k On Day 1 and 42, study drug must be administered in the clinic on an empty stomach (at least 1 hour before breakfast, which will be provided at the site) and the participant should be observed in the clinic for approximately 6 hours before discharge. On all other days, participants should be instructed to take study drug at least 1 hour before breakfast in the morning at home. The escalation schedule is as follows: 20 mg, Day 1 through Day 3; 40 mg, Day 4 through Day 7; 60 mg, Day 8 through Day 14; 80 mg, Day 15 through Day 21; 100 mg, Day 22 through Day 28; and 120 mg, Day 29 through Day 42. Participants will receive blinded study drug on Days 43 to 56. During blinded treatment period, participants should take the same number of tablets per day as taken during Days 36 to 42.

